3.2 Study population

The present study will include all the hereditary haemoglobinopathies (including but not limited to thalassaemia syndromes and SCD) that affect the paediatric population from 1 month to less than 18 years of age and requiring frequent transfusions (at least 150 ml/kg/year of packed red blood cells corresponding approximately to 12 transfusions) and chelation. Chelation naïve patients will be included if they have received at least a quantity of 150 ml of packed red blood cells/kg corresponding to approximately 12 blood transfusions.

3.3 Interventional drugs

Deferiprone is the experimental drug.

Deferiprone will be administered orally at the approved dosage of 75-100mg/kg/day for 7 days per week for the entire duration of the treatment (12 months).

For children from 1 month to less than 6 years, where limited data are available in the SmPC and in literature, the dosage will be derived by the results of an *ad hoc* designed Pharmacokinetic (PK) study sponsored by the same DEEP Consortium (Study DEEP-1, EudraCT n. 2012-000658-67).

The deferiprone formulation to be used in this trial is a new strength (80 mg/mL) of the currently marketed DFP oral solution (Ferriprox® 100 mg/mL oral solution), with some changes in excipients. This lower strength formulation was recently developed by the Marketing Authorisation Holder (MAH) and included in an approved Paediatric Investigational Plan (PIP), and will allow the administration of more accurate volumes in children, minimising the risk of over- or under-dosing. This formulation will also provide the advantage of improved palatability, thus ameliorating objections to the inherently bitter taste of the currently available syrup. Thus, it is expected to improve patients' compliance, and thereby clinical outcomes and quality of life (QoL). For further details please refer to **Section 6.1**.

Deferasirox (Exjade®) is the comparator.

DFX dosage will range from 20 to 40 mg/kg/day as recommended in the SmPC currently approved in Europe (**Annex 1**). For further details please refer to **Section 6.2**.

4. STUDY DESIGN

This is a Phase III study, providing efficacy and safety data after one year treatment with DFP and DFX.

No studies directly comparing DFP and DFX are available. Published literature including the most recent meta-analyses (Roberts D et al, 2007; Maggio A et al, 2010; Meerpohl JJ et al, 2012) compares the efficacy of both IMPs with that of DFO and demonstrate that their efficacy profiles are non inferior to those of DFO. These findings refer mainly to adults but include also some data in the paediatric population. On this basis testing for non-inferiority of DFP versus DFX is well supported.

Thus, this study has been designed as a multicentre, randomized, open label, active comparator controlled, parallel group trial for establishing the non-inferiority of DPF to DFX in terms of changes in ferritin levels and cardiac iron concentration in paediatric patients after 1 year of treatment.

Evidence that serum ferritin is a reliable parameter to evaluate any chelator efficacy has been widely published (Gabutti V and Piga A. 1996; Olivieri, N. et al 1994; Telfer PT, 2000; Borgna-Pignatti, 2004) and represents the basis for monitoring therapy and assessing efficacy particularly in the paediatric population.

However, more recent literature highlights also the important role of cardiac MRI T2* in the understanding and treatment of cardiac siderosis. In the paediatric population iron accumulation in the heart begins to be evident later than in the liver and evidence has been accumulating suggesting that the use of MRI T2* is not of value in chelated patients prior to about 10 years of blood transfusions (Wood JC, 2008, Meloni A., HTA-Thal project funded by Italian Ministry of Health, final project meeting, Rome, June 28, 2011; Guidelines for the clinical management of Thalassaemia, 2nd revised edition, Thalassaemia International Federation, 2008). Moreover, cardiac MRI T2* evaluation has limited application to younger patients unable to undergo the scan without being sedated. For the above mentioned reasons, the performance of a cardiac T2* in children over 10 years is generally recommended in clinical practice, unless clinical condition suggests a cardiac evaluation before that age.

On such evidence, treatment efficacy will be measured in terms of percentage of successfully chelated patients assessed with ferritin and cardiac MRI T2* as defined in **Section 4.3**.

The target patient population consists of 388 outpatients affected by hereditary haemoglobinopathies requiring chronic transfusion and chelation, randomized 1:1 in two groups of 194 patients each to ensure 310 evaluable patients. Chelation naïve and not naïve patients aged from 1 month to less than 18 years will be recruited. A staggered approach will be applied to patients aged less than 6 years (10% of the total sample), which will be recruited after results from the PK Study (Study DEEP-1, EudraCT n. 2012-000658-67) will be available.

Experimental arm: patients administered with DFP at 75-100 mg/kg/day for seven days per week. In patients aged less than 6 years the dose will be defined according to the results of the PK Study (Study DEEP-1, EudraCT n. 2012-000658-67). DFP daily dose will not exceed 100 mg/kg.

Control arm: patients administered with DFX at 20-40 mg/kg/day as recommended by the currently approved European SmPC (last update 10/08/2011). DFX daily dose will not exceed 40 mg/kg.

Details on the starting dose and subsequent dose adjustments are reported in **Section 6**.

The **treatment duration** for both groups is 12 months.

4.1Non-inferiority margin

This study is designed to demonstrate the **non-inferiority** of a new liquid DFP (80 mg/mL) formulation in comparison with DFX in terms of percentage of successfully chelated patients as described in **Section 4.3**.

DFP will be declared non inferior to DFX if the lower limit of the 95% confidence interval for the difference in the proportion of successful chelation in the two groups is above -12.5%. The choice of this margin is based on clinical considerations starting from the available evidences for the effects of DFX at both ferritin and cardiac levels. For details please refer to **Section 11**.

4.2Choice of comparator

DFP will be compared to the oral chelating agent DFX. The rationale for comparing two oral chelators derives from the recent literature data reporting that oral chelating agents currently represent the most widespread adopted therapy in the paediatric age, due to good compliance, improved QoL and reduced burden of the disease (Ceci A et al, 2011).

4.3Primary endpoint

The primary endpoint will be the measure of treatment efficacy defined as the percentage of patients successfully chelated, as assessed by serum ferritin levels (in all patients) and cardiac MRI T2* (in patients above 10 years of age able to have an MRI scan without sedation).

In details, a composite outcome measure will be defined as primary endpoint of the study according to patient's age, as follows:

- in patients < 10 years of age treatment success will be defined only in terms of serum ferritin level (criterion A);
- in patients ≥ 10 years of age treatment success will be defined in terms of both serum ferritin level and cardiac MRI T2* (criteria A and B).

In patients ≥ 10 years of age who would require sedation for the MRI scan, treatment success will be defined only in terms of serum ferritin level (criterion A). Details on the choice of the composite outcome are in **Section 11.1**.

4.3.1 Definition of successful chelation

The following criteria will be used to identify a treatment success:

- Criterion A - Serum Ferritin Levels:** success for patients with baseline serum ferritin levels of 2500 ng/mL or more will be defined as a 20% reduction or more after 1 year treatment. Success for patients with baseline serum ferritin levels less than 2500 ng/mL will be defined as any decrease in serum ferritin, or an increase in serum ferritin, if that increase is less than or equal to 15% of the baseline level, as long as the increase does not result in a serum ferritin above 2500 ng/mL within 12 months despite continual transfusional therapy.
- Criterion B - MRI T2* Cardiac Iron Concentration:** success for patients with baseline values of 20 ms or more will be defined as any increase in T2* or, if there is a decrease, the decline is not more than 10% after 1 year, as long as this does not result in a value below 20 ms. Success in patients with a baseline less than 20 ms will be defined as an increase in T2* of 10% or more despite transfusional therapy.

Table 1 summarises the applied criteria.

Table 1. Definition of treatment success

Baseline ferritin \geq 2500 ng/mL	Reduction of 20% or more after 1 year treatment
Baseline ferritin $<$ 2500 ng/mL	
 any decrease increase \leq 15% as long as the increase doesn't result in ferritin $>$ 2500 ng/ml after 1 year treatment
Baseline MRI T2* $<$ 20 ms	
 Increase of 10% or more after 1 year treatment
Baseline MRI T2* \geq 20 ms	
 any increase decrease \leq 10% after 1 year treatment as long as the decrease does not result in MRI T2* value $<$ 20 ms

4.4 Secondary endpoints

4.4.1 Serum ferritin levels

Serum ferritin levels will be evaluated as secondary endpoint and will be measured in the entire patient population. It is a well validated and clinically accepted surrogate measure of iron load, correlated with LIC, and easily assessed in the paediatric population.

Quarterly blood sampling for ferritin measure is planned both at local and central laboratory/ies level during the 1 year treatment. All formal analyses will be based upon values generated in the central laboratory/ies.

Serum ferritin, as a component of the composite endpoint, will be analysed as secondary endpoint with the intent of clarifying the interpretation of the composite and finally supporting treatment efficacy (Turk DC et al, 2008). Non inferiority of DFP to DFX will be established using ferritin as continuous variable.

In addition, serum ferritin trends over time will be compared to investigate potential difference between DFP and DFX treatments. Details of the analyses are reported in **Section 11.2**.

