The choice of this composite endpoint allows the feasibility of the trial in the entire paediatric population and provides an up to date approach to the evaluation of the global iron accumulation in paediatric transfusion-dependent patients. In addition the use of a composite endpoint (rather than an alternative one) allows avoiding multiplicity while adequately characterising (total body iron load and in the heart) the beneficial effect of treatments.

Each component of the composite endpoint will be considered for secondary analyses with the intent to clarify the interpretation of the composite. For such analyses no adjustment for multiplicity will be foreseen (see **Section 11.2**).

Based on the above defined composite endpoint, non inferiority is established if the lower limit of two sided 95% confidence interval of the difference in success rate is above - 12.5%. The choice of this margin is based on clinical considerations starting from the available evidences for the effects of DFP and DFX on ferritin levels and cardiac iron load.

In details, the percentage of expected success for DFX and DFP measured as change from baseline to 1 year treatment is summarised in the following **Table 6**:

Table 6: Success rates for DFP and DFX

Serum ferritin levels	76% (95%CI: 63.6-88.5) DFP mean dose 66.4 mg/kg/day (Addis A et al, 1999) Paediatric population included in the meta-analysis but not analysed separately.	57% (95%CI: 50.7-63.3) DFX used at 20-30 mg/kg/day (Taher A et al, 2009) 75 adult and 162 paediatric patients
Cardiac MRI T2*	66% Higher percentage in splenectomised patients (Pennell DJ et al, 2006) 29 adults	69.5% in patients with moderate-to-mild baseline cardiac iron load (≥ 10 to <20 ms) DFX mean dose 33.1 \pm 3.7 mg/kg/day (Pennell DJ et al, 2010) 72 adult and 29 paediatric patients

Pooling together these findings, the expected percentage of success in the composite endpoint is assumed to be equal to 65% and 67.5% for DFX and DFP, respectively. The non inferiority margin of 12.5% has been considered to be a good estimate of an achievable lower bound of the true difference between the DFP and DFX.

Other secondary objectives include the evaluation of treatment efficacy in terms of liver iron concentration, the assessment of treatment safety and tolerability profiles, healthcare resources utilisation and patient global assessment and the analysis of the relationship of the demographic covariates and the disposition of DFP.

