11.6 Efficacy evaluation

Primary efficacy

The primary efficacy evaluation will be based on a treatment success rate defined in Section 4.3 Primary endpoint. The primary analysis will be based on the PP1 population.

In addition, an ITT analysis will be performed to corroborate the findings. If no composite endpoint is estimable at 1 year treatment (unavailability of serum ferritin and/or MRI determination either at baseline or after 1 year treatment), the subject is considered a treatment failure in the ITT analysis. Non-inferiority will be assessed based on the two sided 95% confidence interval $[\delta_L, \delta_U]$ of the difference $\delta = p_1 - p_2$, being p_1 and p_2 the proportion of success in the n_1 and n_2 patients randomised to DFP and DFX arms, respectively. Non-inferiority will be claimed if δ_L is greater than -0.125. The two sided 95% confidence interval for δ will be estimated based on asymptotic normal approximation for the difference of two binomial probabilities as follows:

$$(p_1 - p_2) \pm Z_{1-\alpha/2} \sqrt{Var(p_1 - p_2)}$$

where Z_γ is the γ^{th} percentile of the standardised normal distribution and

$$Var(p_1 - p_2) = p_1(1 - p_1)/n_1 + p_2(1 - p_2)/n_2$$

If non-inferiority of DFP to DFX is established based on the PP1 population and the confidence interval for the null hypothesis of non-inferiority based on the ITT population is similar or the percentage of success for DFP is greater than that of DFX in magnitude, the hypothesis that DFP is superior to DFX in terms of the defined success criteria will be tested at the one-sided alpha level of 0.025. Superiority testing will be based on the ITT population. The rationale for superiority is justified by the known beneficial effects of DFP at the cardiac level.

Secondary efficacy

Efficacy measured through serum ferritin levels

Serum ferritin will be analysed as secondary measure of treatment efficacy. Serum ferritin is a well validated and clinically widespread surrogate measure of iron load, highly correlated with iron in the liver. It represents an easy to assess parameter in the paediatric population.

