Serum ferritin will be tested in terms of quantitative variable as part of the composite endpoint measurable in the entire experimental population. The purpose of this analysis is to clarify the interpretation of the primary composite endpoint and hence no adjustment for multiplicity will be considered. The population for this analysis is the PP2. ITT analysis will be used to corroborate the findings.

Non inferiority of DFP to DFX will be tested considering a non inferiority margin of 400 ng/mL.

Non-inferiority will be assessed based on the two sided 95% confidence interval $[\delta_L, \delta_U]$ of the difference $\delta = m_1 - m_2$, being m_1 and m_2 the mean difference between baseline and end of treatment assessments of DFP and DFX, respectively, and n_1 and n_2 the numbers of patients randomised to DFP and DFX arms. Non-inferiority will be claimed if δ_L is greater than -400 ng/ml.

The two sided 95% confidence interval for δ will be estimated as follows:

$$(m_1 - m_2) \pm Z_{1-\alpha/2} \sigma \sqrt{\frac{1}{n_1} + \frac{1}{n_2}}$$

where Z_γ is the γ^{th} percentile of the standardised normal distribution and σ^2 is the pooled variance.

Serum ferritin trends over the 1 year period of treatment will be also investigated. A repeated measures analysis of variance model with treatment-group as main effect will be fitted. The H_0 of equal between group regression slopes will be tested by evaluating whether the interaction between the categorical factor (treatment group) and the repeated measure (monthly measures of serum ferritins) equals zero, i.e. no interaction. The rejection of the null hypothesis on the interaction term (treatment group*monthly ferritin measure) will be supportive of different trends between DFP and DFX arms. The ITT population will be used for this analysis. Handling of missing data for this analysis is described in Section 11.4.

Descriptive statistics for trends in subgroups of patients according to age classes will be also provided.

Efficacy measured through cardiac T2* MRI

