In the last years, the role of cardiac MRI T2* in the management of patients affected by hereditary haemoglobinopathies has been highlighted. Findings are available for the adult population, more limited experience is reported in children. Despite the importance of early detection of cardiac siderosis, MRI is difficult to perform in the paediatric population and it is usually uninformative in younger children (namely less than 10 years) due to late iron accumulation in the heart.

As a consequence, cardiac MRI T2* will be analysed as additional secondary measure of treatment efficacy in the subgroup of patients (over 10 years) for which the scan is available. It will be analysed as binary variable (successfully/unsuccessfully chelated patient according to the criterion 4.3.1 in Section 4.3) as part of the composite endpoint as well as according to its quantitative nature.

Due to the paucity of paediatric data on cardiac MRI T2*, descriptive statistics will be calculated and used to support efficacy conclusions. Descriptive measures will be listed by visit and treatment and characterised by frequency and percentage or mean, standard deviation, median, and quartiles.

However, considering the importance of improving knowledge on iron overload at the heart level in the paediatric population, a test for non inferiority of DFP to DFX in terms of cardiac MRI T2* (successfully/unsuccessfully chelated patient according to the criterion 4.3.1 in Section 4.3 Primary endpoint) will be performed whenever MRI evaluation will be available in at least 60-70% of the evaluable population. See section 11.3 different scenarios (non inferiority margins and sample size) related to this secondary efficacy assessment. The population for this analysis is the PP3.

Efficacy measured through MRI liver iron concentration

Iron overload in the liver compartment will be assessed as additional secondary measure of efficacy. LIC changes within one year will be evaluated in terms of percentage of successfully chelated patients according to the success criterium described in section 4.4.1 Secondary endpoints. LIC absolute values will be also analysed.

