11.12 Sample Size and power considerations

Primary efficacy objective

Assuming type I and type II errors of 0.025 and 0.20, respectively, and a one-sided test, and under the assumptions that the expected proportion of subjects declared treatment successes in the DFX arm is 65%, and the expected proportion of subjects declared treatment successes in the DFP arm is 67.5% a sample size of 310 subjects, randomized in a 1:1 ratio to DFP or DPX will yield 80% power to demonstrate non-inferiority of DFP versus DFX. Taking into account a possible dropout rate of about 20% a total enrolment of 388 patients aged from 1 month to less than 18 years are expected to be included in the trial.

Secondary efficacy objective

Sample size requirements for the secondary efficacy objectives (non-inferiority in terms of ferritin levels and cardiac MRI T2*) are provided in the following.

Based on published literature, testing for non-inferiority is appropriate also when comparing DFP to DFX efficacy in terms of serum ferritin levels. In this case, considering a hypothesis testing on the continuous measure, a non inferiority margin of 400 ng/ml is considered a reliable estimate of the true allowed maximum difference between the IMPs in order to assume DFP to be non-inferior to DFX in controlling iron overload in patients affected by hereditary haemoglobinopathies. The standard deviation of the differences is available by pooling findings from paediatric studies conducted in Europe and outside (El Alfay M et al., 2010), and a reliable and conservative estimate can be 1000 ng/mL.

On these assumptions, 310 evaluable patients are sufficient to provide at least 90% power to demonstrate non inferiority of DFP to DFX, assuming a type I error of 0.025 and a one-sided test.

When considering efficacy in terms of cardiac MRI T2*, less reliable estimates of treatment efficacy are available, especially in the paediatric population. However, there are no reasons for not assuming at least a non inferiority of DFP to DFX, considering also the known beneficial effects of DFP at the cardiac level. Based on the limited published figures of cardiac MRI T2* in the paediatric population and taking into account adult data, some plausible scenarios of sample sizes and related powers are provided in the following **Table 7**, assuming a type I error of 0.025 and a one-sided test. Detailed power curves will be provided in the statistical plan.

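### Ferritin non-inferiority can be formally claimed at one-sided 2.5% after the composite primary endpoint has failed, although the plan justifies the unadjusted analysis as explanatory only

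*Combined protocol and SAP*

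**What the plan says.** Sections 4.1 and 11.1 define one trial-level declaration: DFP is non-inferior if the lower limit of the two-sided 95% CI for the difference in composite success rates lies above -12.5 percentage points.

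For the two components, Section 11.1 describes the analyses as aids to interpreting the composite and adds "For such analyses no adjustment for multiplicity will be foreseen". Section 11.6 repeats that reasoning for ferritin.

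Ferritin nevertheless has a full decision procedure:
- Section 4.4.1: "Non inferiority of DFP to DFX will be established using ferritin as continuous variable".
- Section 11.6: a margin of 400 ng/mL and the rule "Non-inferiority will be claimed if δ_L is greater than -400 ng/ml", read from a two-sided 95% CI in PP2.
- Section 11.12: at least 90% power with 310 evaluable patients, SD 1000 ng/mL, one-sided type I error 0.025.

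No passage makes this test depend on the primary result. The superiority test on the composite, by contrast, is conditional in Section 11.6: "If non-inferiority of DFP to DFX is established based on the PP1 population", with a further condition on the ITT result.

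For cardiac T2*, Section 11.6 plans "a test for non inferiority of DFP to DFX in terms of cardiac MRI T2"*, triggered by scan availability in at least 60-70% of evaluable patients. Table 7 lists margins of -12.5 and -10 points as scenarios.

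**The concern.** The two roles given to ferritin do not fit together. An analysis that explains the composite needs estimates and intervals, and these need no share of alpha. A margin, a power statement and a rule for when a claim is made belong to a confirmatory test. The reason given for waiving multiplicity control covers the first role only.

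What is at stake is the conclusion drawn after a failed primary. The composite carries the cardiac criterion for patients aged 10 or over who can be scanned without sedation, and mean ferritin change does not, so ferritin can pass when the composite fails. Section 2.1 words the primary objective as non-inferiority in ferritin changes and heart iron concentration. A ferritin claim could therefore be mistaken for meeting part of that objective.

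**Working it through.** **Inputs.** From Sections 11.6 and 11.12: "Assuming type I and type II errors of 0.025 and 0.20, respectively, and a one-sided test" for the primary; success rates 65% (DFX) and 67.5% (DFP); primary margin 12.5 points; 310 evaluable patients at 1:1, so 155 per arm; ferritin margin 400 ng/mL, SD 1000 ng/mL, one-sided 0.025. Three inputs are assumptions: a true ferritin difference of 0 (the plan states none), the correlation between the two test statistics, and 155 per arm in both PP1 and PP2.

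**1. The plan's own figures.**
- Primary: SE = sqrt[(0.65×0.35 + 0.675×0.325)/155] = 0.0537. Power = Φ[(0.125 + 0.025)/0.0537 - 1.96] = 79.8%. The standard formula gives 156 per arm, or 312, against the stated 310. 310/0.8 = 387.5, which rounds up to 388.
- Ferritin: SE = 1000×sqrt(2/155) = 113.6. Power = Φ(400/113.6 - 1.96) = 94.1%, consistent with at least 90%.

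The stated figures reproduce, so no sample-size number is in dispute.

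**2. What passes on ferritin.** The CI half-width is 1.96×113.6 = 222.6 ng/mL. The claim is made for any observed DFP shortfall below 400 - 222.6 = about 177 ng/mL, whatever the composite shows.

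**3. Chance of at least one false claim, primary and ferritin, both true differences at their margins.** If independent, 1 - 0.975² = 4.9%. With correlation r it is 1 - Φ₂(1.96, 1.96; r):

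| r | 0 | 0.3 | 0.5 | 0.7 | 0.9 |
|---|---|---|---|---|---|
| At least one false claim | 4.9% | 4.8% | 4.5% | 4.2% | 3.5% |

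**4. Primary fails, ferritin claimed, under the plan's primary assumptions and equal ferritin change.** The primary fails with probability 1 - 0.798 = 20.2%. If independent, 0.202×0.941 = 19.0%. Over all possible dependence, the lower bound is 0.941 - 0.798 = 14.3% and the upper bound is 20.2%. Under a bivariate normal model with r from 0.3 to 0.9 the figure runs from 17.8% to 14.5%. This measures how often the situation would arise. It is not an error rate, because in this scenario DFP is truly within both margins.

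**5. With a gate.** If ferritin can be claimed only after the primary passes, then when the composite null is true any claim requires a false primary pass, at most 2.5%. When only the ferritin null is true, the ferritin test itself errs at most 2.5%. The two-test error is therefore at most 2.5% for any correlation.

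**The case against.** The strongest reply is that the plan discloses and explains its choice. Ferritin is a pre-specified secondary endpoint, no family-wise 2.5% is promised, and whether secondary endpoints need strong error control is partly convention. That stands, and it limits the point to the conflict between the stated purpose and the claim rule. Disclosing the waiver does not remove that conflict. Sections 11.7 and 11.12 mention a further analysis plan, but for safety details and power curves, not for a testing order.

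Four stronger readings are tempting, and the documents do not support them.
- A reader might infer that a failed trial could still declare DFP non-inferior overall. Sections 4.1 and 11.1 rest that declaration on the composite alone.
- A reader might count cardiac T2* as a third equal route and quote 1 - 0.975³ = 7.3%. The T2* test is also ungated, but it depends on scan availability, has no single fixed margin and has no sentence stating when a claim is made. It is a lesser point.
- A reader might infer that the stated 2.5% is wrong. Section 11.12 gives 0.025 separately for each test, and each holds individually.
- A reader might take the 94% chance of a ferritin claim as the harm. That is power at a true difference inside the margin, where the claim is correct by the plan's definition.

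Independence is also implausible, since ferritin is part of the composite for every patient and all of it for those under 10. The 4.9% is therefore an upper value within the range shown.

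**Conclusion.** The concern holds for ferritin, as a component-level claim. The plan permits a formal non-inferiority claim on ferritin after a failed composite, while its reason for not adjusting supports only explanatory reporting. The chance of at least one false claim stays above 2.5% across the assumed correlations from 0 to 0.9. That excess needs both true differences at their margins; if only one is, the figure is 2.5%. The outcome of a failed primary with a ferritin claim is realistic, at roughly one trial in five to one in seven, given the plan's primary assumptions and an assumed equal ferritin change. The primary test, its error rate and the sample size are unaffected. This is an inexpensive improvement worth making, not a defect in the primary inference.

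**What to change.** In Sections 4.4.1 and 11.6, allow a ferritin non-inferiority claim only if composite non-inferiority has been shown in PP1. Otherwise report the ferritin difference with its 95% CI and make no claim. Removing the ferritin claim wording altogether would also resolve the conflict.

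State where the already gated composite superiority test falls relative to ferritin. If both were opened at full 2.5% after the primary, the same arithmetic (1 - 0.975²) would again allow up to about 4.9% for that pair if independent.

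Report T2* as an estimate with its 95% CI, or place it last in the order with one pre-fixed margin and one availability threshold in place of the 60-70% range.

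The cost is a wording amendment, loss of the ferritin claim if the primary fails, and loss of any later step when an earlier one fails, even if the primary passed. Primary alpha and power and the 310 evaluable and 388 enrolled patients stay as they are. Splitting alpha would be more expensive: at 0.0125 per test the primary has 71.0% power with 310 evaluable patients and needs 378 for 80%.
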